attributed to the development of electrolyte disturbances. Dose interruption or reduction, or permanent discontinuation of cabozantinib should be considered in case of persistent or recurrent significant abnormalities (see section 7.1.2).

15) Osteonecrosis of the Jaw

Osteonecrosis of the jaw (ONJ) occurred in <1% of patients treated with cabozantinib. ONJ can manifest as jaw pain, osteomyelitis, osteitis, bone erosion, tooth or periodontal infection, toothache, gingival ulceration or erosion, persistent jaw pain or slow healing of the mouth or jaw after dental surgery. Perform an oral examination prior to initiation of cabozantinib and periodically during cabozantinib. Advise patients regarding good oral hygiene practices. Withhold cabozantinib for at least 28 days prior to scheduled dental surgery or invasive dental procedures, if possible. Withhold cabozantinib for development of ONJ until complete resolution.

16) Embryo-Fetal Toxicity

Based on data from animal studies and its mechanism of action, cabozantinib can cause fetal harm when administered to a pregnant woman. Cabozantinib administration to pregnant animals during organogenesis resulted in embryolethality at exposures below those occurring clinically at the recommended dose, and in increased incidences of skeletal variations in rats and visceral variations and malformations in rabbits.

Advise pregnant women of the potential risk to a fetus. Advise females of reproductive potential to use effective contraception during treatment with cabozantinib and for 4 months after the last dose.

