7.2.2. Atezolizumab dose modifications

There will be no dose reduction for atezolizumab in this study. Patients may temporarily suspend study treatment if they experience toxicity that is considered to be related to study drug and requires a dose to be held. If atezolizumab is held because of related adverse events for 42 days beyond when the dose would have been given, then the patient will be discontinued from atezolizumab and will be followed for safety and efficacy as specified in section 8. Please see Section 7.2.3 for guidelines for the management of infusion related reactions.

Dose interruption of atezolizumab

Any toxicity observed during the study treatment phase could be managed by interruption of the dose of the study treatment if deemed appropriate by the Investigator. Repeated dose interruptions are allowed as required, for a maximum of 42 days on each occasion. If the interruption is any longer than this, the Coordinating Investigator must be informed and treatment restart should be discussed between the Sponsor study team and the investigator. If in the judgment of the investigator, the patient is likely to derive clinical benefit from resuming atezolizumab after a hold of 42 days, the treatment may be restarted with the approval of the Coordinating Investigator.

If patients must be tapered off steroids used to treat adverse events, study treatment may be held for 42 days. The acceptable length of interruption will depend on agreement between the investigator and the Coordinating Investigator.

Study treatment must be interrupted until the patient recovers completely or the toxicity reverts to the National Cancer Institute Common Terminology Criteria for Adverse Events (NCI CTCAE version 5.0) grade 1 or less.

Treatment with atezolizumab must be temporarily or permanently interrupted if any NCI CTCAE grade 3 or 4 adverse event occurs which the Investigator considers to be related to the administration of atezolizumab. Dose interruptions for reason(s) other than toxicity, such as surgical procedures, may be allowed. The acceptable length of interruption will depend on agreement between the investigator and the Coordinating Investigator.

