If atezolizumab is temporarily or definitively interrupted for its toxicity, cabozantinib will be continued, unless the toxicity of atezolizumab prevents the administration of cabozantinib or increase the risk of cabozantinib toxicity. In this case, both treatments will be interrupted until toxicity resolution (or NCI CTCAE grade 1) or definitively.

If one of the two drugs is discontinued or interrupted due to toxicity, the administration of the other drug should continue according to the protocol schedule.

All dose reductions and interruptions (including any missed doses), and the reasons for the reductions/interruptions are to be recorded in the eCRF and patient record. An occurrence of autoimmune disease will be declared in this study as a serious adverse event (SAE) at any time during atezolizumab treatment and at any time after the treatment has been stopped.

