8. STUDY ASSESSMENTS

8.1. SCHEDULE FOR TESTS AND DETERMINATIONS

Study assessments should be performed following the indications of this schedule of determinations and when clinically indicated according treating clinician (i.e: more frequent determinations in case of toxicities).

Table 2. Schedule for test and determinations throughout the study period

	Screening	C1	C2	C3	C4	C5	C6	C7 to PD	EOT	Up to EOS	
Week	-4 To -1	0	Q3w ±3 days unless dosing needs to be held for toxicity reasons				Q3w ±3 days unless dosing needs to be held for toxicity reasons				
Day	-28 To -1	1 ^a	Q21 Days ±3 days unless dosing needs to be held for toxicity reasons				Q21 Days ±3 days unless dosing needs to be held for toxicity reasons				
Informed Consent											
Informed Consent ^b	X										
Consent and Collection of Specimens for Future Biomedical Research	X										
Study Procedures											
Medical History	X										
Physical Exam (Full)	X										
Targeted Physical Exam (Based On Symptoms)		X	X	X	X	X	X	X	X		
Vital Signs ^c	X	X	X	X	X	X	X	X	X		
ECG ^d	X	As clinically indicated							X		
Prior and Concomitant Medications	<----->										
Demography, Including Baseline Characteristics And Tobacco Use	X										
Eligibility Criteria	X										
Laboratory Assessments											
Clinical Chemistry ^e	X	X ^f	X	X	X	X	X	X	X		
Hematology ^e	X	X ^f	X	X	X	X	X	X	X		
TSH ^g (Reflex Free T3 Or Free T4 ^h)	X	X	X	X	X	X	X	X	X		
Hepatitis B, C and HIV ⁱ	X										
Urinalysis	X									X	
Tumor markers ^q	X	q12w ± 2w until objective disease progression or death (whichever occurs first).									
Pregnancy Test ^j	X	If clinically indicated									
Monitoring											
ECOG Performance Status	X	X	X	X	X	X	X	X	X		
QoL (EQ-5D-5L, EORTC QLQ-C30) ^p	X		X		X		X	q6w		X	
AE/SAE/AESI Assessment ^k		X	X	X	X	X	X	X	X		
Post-treatment Follow-up ^l										X	
IMPs Administration											
Cabozantinib ^m			X (p.o. daily, until PD or unacceptable toxicity)								
Atezolizumab ^m			X (IV. q3w, 21 days ±3 days until PD or unacceptable toxicity)								
Biological samples collection											
Tumor Biopsy (Archival, If Available)	X										
Processed blood samples ⁿ	X		X							X	
Efficacy Evaluations											
Tumor evaluation (CT scan or MRI) (RECIST 1.1) ^o	X	q12w ± 2w until objective disease progression/death (whichever comes first).									

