- j) Women of childbearing potential are required to have a pregnancy test within 72 hours prior to the first dose of the study drug, and every 3 cycles (9 weeks) thereafter (if clinically indicated). Latest pregnancy results (maximum 9 weeks old) must be available and reviewed by the treating physician or investigator prior to commencing a new cycle of infusion. A urine or serum pregnancy test is acceptable.
- k) For AEs/SAEs reported during screening, additional information such as medical history and concomitant medications may be needed.
- l) Post-treatment follow up: all patients will be followed up according to RECIST 1.1 every 12 weeks (+/-14 days) up to disease progression or death (whichever occurs first), regardless of the reason for ending the treatment. Follow up assessments may be performed q8w ± 2w if required by local standard clinical practice or by investigator criteria, as long as the frequency of assessments is maintained. Neuroendocrine markers are to be analysed according to local practice. The follow-up period according to this protocol is 12 months considering last patient inclusion. Information on subsequent treatments should include the list of post-treatment therapies, the drugs administered, and the date of initiation and discontinuation of each drug. All the data will be recorded in the medical record and in the eCRF.
- m) The initial dose of atezolizumab will be administered before cabozantinib and must be administered over 60 minutes. If the first infusion is well tolerated, all subsequent infusions may be administered over 30 minutes. For the rest of the cycles, cabozantinib will be self-administered by the patients daily and as per principal investigator indications. Results for LTFs, electrolytes, and creatinine must be available before commencing an infusion (within 3 days) and reviewed by the treating physician or investigator prior to dosing.
- n) Biomarker study: Collection of the most recent archived tumour-biopsy sections. Processed blood samples at baseline, day 1 of cycle 2 (D1C2), at EOT/progression. Blood samples should be obtained in all patients at the time of EOT (even by toxicity without progressing) and samples are to be stored at site at -80 °C and are to be sent at the end of study (1 dry ice shipment per site).

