The investigator or qualified designee will review prior medication use including any protocol-specified washout requirement, and record prior medication taken by the subject within 4 weeks of first dose of the study treatment.
- *Concomitant Medications:*
 - The investigator or qualified designee will record the medication, if any, taken by the subject during the trial from the time of signing the informed consent form until the Safety Follow-up Visit.
 - All medications related to reportable SAEs should be recorded
 -

Demography, Including Baseline Characteristics And Tobacco Use

- Date of birth (month/year of birth) or age at informed consent, race, and sex.
- Smoking history: never smoke (≤ 100 cigarettes/life time), former smoker (≥ 1 year), smoker, unknown)
- Tobacco use: pack/year and cigarettes/day.

Eligibility Criteria

All inclusion and exclusion criteria will be reviewed by the investigator or qualified designee to ensure that each subject qualifies for the trial. More details on criteria for patients' eligibility are in section 6.1 and 6.2.

Laboratory Assessments

The summary of the procedures required is summarised in Table 2 and flow chart (Section 8.1 and the corresponding footnotes). Laboratory tests for screening should be performed within 7 days prior to study enrolment. If performed < 14 days prior to the first dose of trial therapy, the screening laboratory tests will serve as cycle 1 day 1 laboratory tests. If not, laboratory tests will need to be performed again on day 1 of cycle 1. Laboratory determinations include full clinical chemistry panel (including albumin, alkaline phosphatase, LDH, calcium, magnesium, phosphorus, sodium, potassium, creatinine, creatine kinase, direct bilirubin, indirect bilirubin, total bilirubin, total protein, urea, uric acid, amylase, lipase, glucose, ALT, AST, ALP, GGT), hematological counts (total white blood cell count with leukocyte formula, haemoglobin, and platelet count), TSH hormone levels, serology (HIV, HBV, and HCV), urianalysis and tumor markers (NSE in tumors from cohort 1, CGA in tumors from cohort 5, cortisol in functionant tumors from cohort 3, metanephrides and, adrenaline in functionant tumors from cohort 4. Norepinephrine, 5-HIAA and CEA may be collected when considered).

Pregnancy test

A serum pregnancy test must be performed at screening (at the local laboratory) within ≤ 72 hours before the *first dose of study treatment (if clinically indicated)*.

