- The investigator or qualified designee will assess each subject to evaluate for potential new or worsening AEs as specified in the Trial Flow Chart, and subsequently if clinically indicated.
- Adverse events will be graded and recorded throughout the trial and during the follow-up period according to NCI CTCAE Version 5.0. Toxicities will be characterised in terms of seriousness, causality, toxicity grading, and action taken with regard to trial treatment.
- All AEs of unknown etiology associated with study treatment exposure should be evaluated to determine if it is possibly an ECI of a potentially immunologic etiology (termed immune-related adverse events, or irAEs).

Tumour Imaging

- q12w \pm 2w until the objective disease progression or death (whichever comes first). Image assessments by CT scan or MRI may be performed q8w \pm 2w if required by local standard clinical practice or by investigator criteria, as long as the frequency of assessments is maintained.

Biological samples collection

Processed blood samples:

- Serum and plasma samples to be collected at D1C2.
- Blood samples are to be stored at site at -80 °C and are to be sent at the end of study (1 dry ice shipment per site).

Pregnancy test

Women of childbearing potential are required to have a pregnancy test within 72 hours prior to the first dose of the study drug, and every 3 cycles (9 weeks) thereafter (if clinically indicated). Latest pregnancy results (maximum 9 weeks old) must be available and reviewed by the treating physician or investigator prior to commencing a new cycle of infusion. A urine or serum pregnancy test is acceptable.

Quality of life

The questionnaires EQ-5D-5L and EORTC QLQ-C30 will be fulfilled every two cycles by the patient during the visit, before the knowledge of tumor assessment and before the administration of each dose of atezolizumab as specified in the Table of Schedule of Assessments (Table 2).

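### Repeat pregnancy testing is optional in one sentence and required in the next, and no fixed-interval test is required once cabozantinib continues without atezolizumab

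*Combined protocol and SAP*

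**What the plan says.** Footnote j to Table 2 (protocol 8.1) applies to women of childbearing potential. It asks for a test within 72 hours before first dose and then "every 3 cycles (9 weeks) thereafter (if clinically indicated). Latest pregnancy results (maximum 9 weeks old) must be available and reviewed" by the physician or investigator "prior to commencing a new cycle of infusion". Section 8.2.2 repeats both sentences, including "every 3 cycles (9 weeks) thereafter (if clinically indicated". The Pregnancy Test row of Table 2 shows, after screening, only "If clinically indicated". SAP 1.3.2 carries the same row and footnote.

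The pre-dose test in 8.2.1 has the same condition, "first dose of study treatment (if clinically indicated", but does not name the population.

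On stopping one drug, 7.2.2 says: "If atezolizumab is temporarily or definitively interrupted for its toxicity, cabozantinib will be continued". The proviso is that both drugs stop if the atezolizumab toxicity rules out cabozantinib or raises its risk. On holds, the same section says: "Repeated dose interruptions are allowed as required, for a maximum of 42 days on each occasion". Section 7.1.3 warns that "cabozantinib can cause fetal harm when administered to a pregnant woman".

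For men, inclusion criterion 10 (synopsis and 6.1) ends contraception 4 months after study participation. Section 9.6.1 ends condom use 5 months after the last dose.

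**The concern.** Footnote j and 8.2.2 already limit themselves to women who could become pregnant, so the condition cannot be shorthand for that population. It can only make the repeat test a matter of judgement. A site that schedules from the Table 2 row would then miss tests that the following sentence demands, and would collect protocol deviations.

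The larger issue is the trigger. Atezolizumab is the only infused drug, so a check before each infusion lapses when infusions pause or end. The patient may still be taking cabozantinib every day. Section 9.6.1 takes a pregnant patient off treatment, which helps only if the pregnancy is detected.

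The male rules give sites two end dates on two different clocks, with no statement of which prevails.

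**Working it through.** **Inputs.** Cycle length 21 days, ±3 days per visit (Table 2). Baseline test at most 72 hours, that is 0–3 days, before first dose (footnote j). Result limit 9 weeks = 63 days (footnote j). Atezolizumab hold of up to 42 days beyond the due date (7.2.2).

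**Consistency of the two intervals.** 3 cycles × 21 days = 63 days = 9 weeks, so the footnote's two intervals agree with each other. The conflict is only between optional and required.

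**Age of the baseline test at a later cycle c.** There are c − 1 intervals. Nominal age is 21(c − 1) to 21(c − 1) + 3. With the full visit windows it is 18(c − 1) to 24(c − 1) + 3.

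| Cycle | Nominal age (days) | Any permitted timing (days) | Limit |
|---|---|---|---|
| 4 | 63–66 | 54–75 | 63 |
| 5 | 84–87 | 72–99 | 63 |

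At cycle 4 the baseline result is at or past the limit on nominal timing. At cycle 5 even the shortest permitted timing (72 days) exceeds it. A woman still receiving infusions at cycle 5 must have been retested, whether or not anyone judged it indicated.

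**One 42-day hold, cabozantinib continued.** The gap between infusions is 21 + 42 = 63 days. The result's age just before the resumed infusion is its age at the last infusion plus 63:

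- tested on the day of the last infusion: 0 + 63 = 63 days, still within the limit;
- already at the limit at the last infusion: 63 + 63 = 126 days, or 18 weeks.

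So the range is 63–126 days, and 126 is the worst case for one such hold.

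**Atezolizumab stopped for good, cabozantinib continued.** There is no further infusion, so the required check never falls due again. Only the conditional three-cycle test is left.

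**Men.** Let G be the months from last dose to the end of participation. Criterion 10 ends at G + 4 and 9.6.1 ends at 5, both counted from last dose. The difference is G − 1: one month shorter at G = 0, equal at G = 1, longer beyond that.

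**The case against.** The best defence is that the required sentence already forces a retest by about cycle 4 or 5, so while infusions continue the condition is redundant wording and the ages above do not measure unmonitored exposure. That stands, provided sites follow the sentence rather than the table row. Contraception is also mandatory for women until 5 months after the last dose, so testing is a second safeguard.

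Some stronger readings are tempting and not supported:

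- *No check at all on cabozantinib alone.* The conditional three-cycle test is not tied to infusion and visits continue every 3 weeks (5.1). What is missing is a required, fixed-interval test.
- *Eighteen weeks as a typical lapse.* It needs a result exactly at its limit, a full 42-day hold, cabozantinib continued throughout and no discretionary test. Cabozantinib does not always continue, because of the proviso in 7.2.2.
- *The gap extends into drug supply after last patient last visit.* Table 2 runs only to end of study. Sections 6.5 and 9 describe supply and event reporting after that, with no testing schedule, so footnote j cannot be faulted there.
- *Criterion 10 is always a month too short for men.* Participation usually outlasts dosing: patients who stop without progression stay in follow-up (5.5.1), and 9.5 refers to a 100-day visit. A man followed to day 100, which is more than 3 months, and then for 4 more is past 7 months.

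**Conclusion.** The point holds in two parts. First, the condition contradicts the requirement beside it. This is certain from the text, and the baseline result is out of date by cycle 5 under any permitted timing. Second, once atezolizumab is held or stopped and cabozantinib continues, no required fixed-interval pregnancy test applies. Permanent discontinuation of atezolizumab is the firmest case. A single 42-day hold gives a result up to 126 days old only at worst.

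The male contraception mismatch is minor. Both rules can be met by following the later date, but the text does not say so.

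The arithmetic assumes 21-day cycles, a baseline test 0–3 days before first dose and, for the hold, nominal timing otherwise. The documents do not give the number of women of childbearing potential or how many would continue on cabozantinib alone, so patients affected cannot be estimated. Nothing here touches the response rate, the two-stage rule or the error rates. It is a patient-safety and consistency point that should be corrected because correction is cheap.

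**What to change.** 1. Remove "If clinically indicated" from the Table 2 row, footnote j and 8.2.2. Require, for women of childbearing potential, a test within 72 hours before first dose and at least every 9 weeks while on either study drug, including cabozantinib alone. Keep the review of a result no more than 9 weeks old before each infusion.
2. In 8.2.1, replace the condition with a limit to women of childbearing potential. Simply deleting it would, read literally, require the test of every patient, because that paragraph names no population.
3. As a secondary alignment, state one rule for men in criterion 10 (synopsis and 6.1) and in 9.6.1: at least 5 months after the last dose of study treatment, without shortening any longer period that criterion 10 already gives. A flat 5 months would cut the period for men whose participation runs more than a month past last dose.
4. Carry the schedule wording into SAP 1.3.2 for consistency.

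The cost is protocol wording plus one urine or serum test about every 9 weeks during cabozantinib-alone periods, done at the existing 3-weekly visits. During infusions the 9-week limit already implies the test.

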Study treatment will begin as soon as possible after signing the informed consent (as per section 5.2 of this protocol) and inclusion will be completed as per section 5.3 of this protocol.

The first administration of cabozantinib will be carried out after the infusion of the first atezolizumab cycle, the patient will take the treatment in the presence of a member of the Site staff who will advise the patient on the correct intake of the treatment (according to the indications of the section 7.1 of this protocol), discuss with the patient the process of completing the patient diary, and address the doubts that the patient may have at the time. In addition, patient must bring all medication bottle(s) (including empty ones) to each visit, for IMP adherence and compliance traceability purposes.

After the first supervised administration, cabozantinib will be self-administered by patients daily according to the indications of the Investigator staff and as indicated in section 7 of this protocol. Treatment with cabozantinib will be continuous until the progression of the disease and/or unacceptable toxicity, among others. Patients will attend follow-up visits with the study doctor every 3 weeks for clinical assessment, laboratory tests, laboratory determinations should be made within 72 hours prior to the date of administration of atezolizumab, in order to assess the relevance of administration of a new cycle (modifications, delays, etc.), according to what is specified in sections 7.1.2 and 7.2.2. Additionally, the study doctor may request patients to come to the centre more frequently in case of toxicity or discomfort of the patient. Additional information about the study's determinations is found in section 8 of this protocol.

Treatment and study determinations will be the same for all the patients, regardless of the cohort in which the patients are included.

This is a study with Simon's two-stage design; it requires that an event is observed in the first nine patients before continuing to the second stage where there is a possible inclusion of 15 additional patients (up to a maximum of 24 patients per cohort).

In addition, an optional biomarker study with tumour and blood samples will be performed (if it is feasible for the Sponsor), and it is detailed in the corresponding biological samples manual.

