5.4. PATIENT TREATMENT

All the subjects will be treated with the combination until disease progression, unacceptable toxicity, or patient consent withdrawal (whichever occurs first) according to section 7 of this protocol.

- Cabozantinib 40 mg or 20 mg tablets, oral administration once daily continuously.
- Atezolizumab 1200 mg administered intravenously (IV) every three weeks (cycle).

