- o) CT Scan or MRI is to be performed at baseline and q12w ± 2w until the objective disease progression or death (whichever comes first). Image assessments by CT scan or MRI may be performed q8w ± 2w if required by local standard clinical practice or by investigator criteria, as long as the frequency of assessments is maintained. The schedule of q12w ± 2 week (q8w ± 2w when applicable) must be followed regardless of any delays in dosing, in case of suspected pseudo-progression; treatment should be continued until progression of disease is confirmed from the imaging results. RECIST assessments will be performed on images from CT scans (preferred) or MRI, each preferably with IV contrast of the neck, chest, abdomen (including liver and adrenal glands), and pelvis. Pelvic imaging is recommended only when primary or metastatic disease in the pelvic region is likely. Additional anatomy should be imaged based on signs and symptoms of individual patients at baseline and follow-up. Baseline assessments should be performed no more than 28 days before the date of inclusion and, ideally, should be performed as close as possible to and prior to the start of treatment.
- p) EQ-5D-5L and EORTC QLQ-C30 Questionnaires (appendix 2 and 3) will be done prior to the start of treatment (at screening) and every 2 cycles (q6w, 42 days) thereafter until PD.
- q) Tumor markers should be analyzed at screening and every 12 weeks ± 2 weeks to determine the non-radiological response. The markers to collect are NSE in tumors from cohort 1, CGA in tumors from cohort 5, cortisol in functionant tumors from cohort 3, metanephrines and adrenaline in functionant tumors from cohort 4. Norepinephrine, 5-HIAA and CEA may be collected when considered.

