- o) CT Scan or MRI is to be performed at baseline and q12w ± 1w until the confirmation of objective disease progression or death (whichever comes first). The schedule of q12w ± 1 week must be followed regardless of any delays in dosing, in case of suspected pseudo-progression; treatment should be continued until progression of disease is confirmed from the imaging results. RECIST assessments will be performed on images from CT scans (preferred) or MRI, each preferably with IV contrast of the neck, chest, abdomen (including liver and adrenal glands), and pelvis. Pelvic imaging is recommended only when primary or metastatic disease in the pelvic region is likely. Additional anatomy should be imaged based on signs and symptoms of individual patients at baseline and follow-up. Baseline assessments should be performed no more than 28 days before the date of inclusion and, ideally, should be performed as close as possible to and prior to the start of treatment. The confirmatory scans should be performed preferably at the next scheduled imaging visit and no less than 4 weeks after the prior assessment of PD (in the absence of clinically significant deterioration). If an unscheduled assessment was performed and the patient has not progressed, every attempt should be made to perform the subsequent assessment at the next scheduled visit.

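### In suspected pseudo-progression, Table 2 footnote o continues treatment until imaging confirms progression, while the other treatment rules stop at progression and the protocol, unlike the SAP, names no confirmatory scan

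*Combined protocol and SAP*

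**What the plan says.** **When treatment stops.** Protocol section 5.4 states: "All the subjects will be treated with the combination until disease progression, unacceptable toxicity, or patient consent withdrawal (whichever occurs first". The synopsis says the same under duration of treatment. Section 5.1 says: "Treatment with cabozantinib will be continuous until the progression of the disease and/or unacceptable toxicity, among others". In the body of Table 2 the cabozantinib row reads "X (p.o. daily, until PD or unacceptable toxicity", and the atezolizumab row has the same end point. SAP section 2.3 repeats the rule of 5.4. None of these places mentions an exception.

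Footnote o to the same Table 2 says that "in case of suspected pseudo-progression; treatment should be continued until progression of disease is confirmed from the imaging results". The SAP's copy of the schedule (section 1.3.2, footnote o) carries the same clause.

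**When imaging stops.** Protocol footnote o says: "CT Scan or MRI is to be performed at baseline and q12w ± 2w until the objective disease progression or death (whichever comes first". Sections 8.2.2, 8.2.4.1 and 10.3 also end RECIST imaging at progression, and section 8.2.4.2 leaves follow-up after progression to local practice. The SAP differs. Its schedule runs imaging until progression is confirmed, and its footnote o adds: "The confirmatory scans should be performed preferably at the next scheduled imaging visit and no less than 4 weeks" after the assessment that showed progression.

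**The concern.** When a scan meets the criteria for progression but the investigator suspects pseudo-progression, section 5.4 tells the site to stop and footnote o tells it to continue. A site cannot do both. The protocol makes the end of treatment depend on confirmation, but it names no confirming scan, and it defines neither suspected pseudo-progression nor confirmed progression. The RECIST tables in section 10.3.1 have no category for unconfirmed progression.

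Three things depend on which rule a site follows:

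- exposure to both drugs after a first progression;
- the date and reason for end of treatment, and treatment length, which SAP section 2.3.7 reports overall and by cohort;
- the start of the 30-day window for adverse events and the 100-day window for serious events and events of special interest, which sections 9.2.1.1, 9.3.2 and 9.5 tie to permanent discontinuation.

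The tables of treatment length and of reasons for stopping would then partly reflect how each site read the protocol.

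**Working it through.** The plan states no figure on this point, so the check is a comparison of text followed by simple interval arithmetic.

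**Step 1: the rules side by side**

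| Question | Protocol 5.4, 5.1, synopsis, Table 2 drug rows; SAP 2.3 | Protocol footnote o | SAP 1.3.2, schedule and footnote o |
|---|---|---|---|
| Treatment ends | At progression | In suspected pseudo-progression: when imaging confirms progression | Drug row: at progression. Footnote: as protocol footnote o |
| Scheduled imaging ends | Not addressed in these treatment rules | At objective progression or death | At confirmed progression or death |
| Confirmatory scan | None | None named | Preferably the next scheduled visit, at least 4 weeks after progression |
| Scan interval | Not addressed in these treatment rules | 12 weeks ± 2, or 8 weeks ± 2 | 12 weeks ± 1, no 8-week option |

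For a patient in whom pseudo-progression is not suspected, the treatment rules agree. They conflict only when it is suspected. The documents also disagree on whether imaging ends at first or at confirmed progression.

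**Step 2: size of the difference if confirmation waits for the next scheduled scan**

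Inputs: scan interval and visit window from the two schedules; cycle length 3 weeks. The nominal gap is the interval. If both visits use the full window in opposite directions, the gap is the interval ± 2 × window. Cycles = weeks / 3.

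- Protocol, 12 weeks ± 2: nominal 12 weeks, 12/3 = 4 cycles. Range 12 − 4 = 8 to 12 + 4 = 16 weeks, or 8/3 = 2.7 to 16/3 = 5.3 cycles.
- Protocol, 8 weeks ± 2: nominal 8 weeks, 8/3 = 2.7 cycles. Range 8 − 4 = 4 to 8 + 4 = 12 weeks, or 4/3 = 1.3 to 12/3 = 4 cycles.
- SAP, 12 weeks ± 1: nominal 12 weeks, 4 cycles. Range 12 − 2 = 10 to 12 + 2 = 14 weeks, or 10/3 = 3.3 to 14/3 = 4.7 cycles. The SAP's minimum is 4 weeks.

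**Step 3: one patient**

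A week-12 scan shows a new lesion, which is progression under section 10.3.1, and the investigator suspects pseudo-progression. Under 5.4 both drugs stop at week 12. Under footnote o, with the next nominal scan as the confirming one, they stop at about week 24 if it confirms progression. The start of both safety windows moves by the same 12 × 7 = 84 days.

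**Step 4: what does not move**

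Section 10.2.2 dates PFS to the first documented progression, so neither rule alters the definition. The sample size uses only 5% against 20%, the error rates and the two-stage thresholds. Going on with at least 1 response in 9 and declaring success with at least 3 in 24 gives alpha 0.093 and power 0.805, within the stated 0.1 and 80%. No stopping rule for treatment enters that calculation.

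**The case against.** The best defence is that a specific footnote can qualify a general rule, so footnote o is simply the exception to 5.4. The same sentence also says: "The schedule of q12w ± 2 week (q8w ± 2w when applicable) must be followed regardless of any delays in dosing". As punctuated, that clause can be tied to suspected pseudo-progression, which would make the next scheduled scan the confirming one. A site could also hold that suspected pseudo-progression is not yet objective progression. The introduction to section 8.1 allows assessments when clinically indicated, and the SAP describes the confirmatory scan.

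Much of this stands, and it rules out two stronger readings. A reader might infer that footnote o keeps every progressing patient on treatment; its wording limits it to suspected pseudo-progression. A reader might also infer that confirmation is impossible; the routes just listed show that a scan can be obtained.

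The defence does not remove the conflict. Section 5.4 covers all subjects and refers the reader to section 7, which says nothing on pseudo-progression. The routes also lead to different dates: an unscheduled scan, a scan at least 4 weeks later, or a full interval.

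It is also fair to say that the safety windows follow actual exposure and are defined under either rule. They are not broken; they start at different times for the same scan.

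**Conclusion.** The conflict is real and confined to suspected pseudo-progression. The protocol keeps a confirmation condition without naming the scan, and the SAP differs from it on where imaging ends. If confirmation waits for the next scheduled scan, the two rules differ nominally by 12 weeks or 4 cycles (8 to 16 weeks), or by 8 weeks on the 8-weekly option (4 to 12 weeks). These ranges assume that both visits may use their full windows; an earlier unscheduled scan would shorten the gap. The documents do not say how many patients would be labelled as suspected pseudo-progression, so the effect on cohort summaries cannot be sized.

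A reader might infer damage to PFS or to the two-stage design. The documents do not support that: PFS is dated to first documented progression, and the sample size does not depend on when treatment stops. Nor should the gap be set against the 5-month median survival quoted for anaplastic thyroid cancer in section 2.1. That is background survival for the disease, not survival of trial patients after a first progression.

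**What to change.** The sponsor should reconcile the synopsis, sections 5.1, 5.4 and 8.2.4.2, and Table 2 with footnote o in the protocol, together with sections 1.3.2 and 2.3 of the SAP. The treatment-stopping rule and the end of scheduled imaging should then agree within the protocol and between the two documents. If suspected pseudo-progression and confirmed progression remain as terms, they need definitions. This review does not say which stopping rule is right.

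For analysis, derive treatment past first progression from the dosing dates and the first progression date. Sections 7.1.2, 7.5 and 7.6.1 already send drug administration, dose changes and interruptions to the eCRF, and PFS already needs the progression date, so nothing in the documents shows that a new field is required. The cost is a protocol clarification, a matching SAP edit and one derived variable.
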